### I. Hypotheses and Specific Aims:

We have previously shown that 83% of patients after Cesarean section and 71% of thoracic surgery report taking half or less of opioids prescribed; 53% and 45% respectively report taking five or less of the prescribed pills. Such overprescribed opioids are stored in unsecured locations in the 75% of cases. These opioids represent a major source of potential morbidity and mortality. The *rationale* that underlies the proposed research is that once we have proven the efficacy of patient-centered pain management approaches, we can improve surgical pain therapy on a large scale.

**Specific Aim:** We will utilize the electronic health record to individualize pain therapy in surgical patients after hospital discharge using last 24-hour opioid intake as the decision variable for the amount of opioid pain pills prescribed. Our preliminary data indicate that current opioid prescription practice after surgery follows a “one size fits all” pattern. In-hospital opioid use 24 hours prior to discharge serves as a strong indicator to correctly estimate needs for analgesic medications at home. We will test our hypothesis that this tool will reduce the amount of opioid medications prescribed while maintaining patient post-operative pain control. We will test this tool prospectively for 44 post Cesarean section patients anticipated to use about half or less of the usually prescribed amount of opioid pain pills randomized equally to prescription tool intervention or no intervention (prescription as usual).

This protocol addresses only Specific Aim #3 of the original grant. Specific Aim #1 and #2 are addressed under a separate COMIRB protocol #14-1938.

### II. Background and Significance:

Prescription opioid overdose has emerged as a leading cause of death in the general population. Opioid-based therapy represents a corner-stone of post-operative pain management. With increasing emphasis on robust pain therapy, sales of opioid medications have increased four-fold in the last decade. Parallel to this rise, opioid-associated deaths have also quadrupled. We have shown that long-term opioid use occurs in up to 22% of patients following surgery. Over-prescribed opioids after surgery can create a reservoir of opioids that become available for non-medical use. Effective strategies to maximize non-opioid pain therapy and to limit such a reservoir are lacking. Thus, there is an *urgent need* to individualize post-operative pain therapy and reduce our reliance on opioids.

Converting knowledge on actual need for opioid pain medications after surgery into tangible benefits can prevent over-prescription of opioids that become available for non-medical use. The *objective* of this aim is to prescribe pain medications after surgery in a patient-centered fashion. We will use the average amount of opioid medications (in oral morphine equivalents - OME) taken in the last 24 hours prior to discharge to inform and design a clinical decision support tool. This tool will reduce the amount of opioid medications prescribed while maintaining patient post-operative pain control. The calculated “last 24 hour OME dose” will be applied to generate a recommendation for the prescription of a cumulative opioid dose that will be shared with the provider when the post-discharge pain medication is made, e.g. via displaying the last 24-hour opioid use in the electronic health record (EHR). The *rationale* is that testing of such a decision-making tool will lay the groundwork to translate the findings of this project into more secure and efficient opioid prescribing practices to a system-wide level. Upon completion, we *expect* to have developed an effective decision-making tool to help providers estimate required pain medication following patient discharge.

### III. Preliminary Studies/Progress Report:

**Preliminary Studies.** In a cohort of 652 patients who had undergone surgery at UCH Metro clinicians chose the same cumulative opioid dose (300 oral morphine equivalents) in more than 75% of patients for the discharge opioid prescription (Figure 1). These data indicate that opioids following inpatient surgery are not prescribed in an individualized fashion, but rather that most patients receive a very similar regimen for post-discharge pain management. Using the same EHR (Epic) database that generated the data above, we are able to generate information on types and doses of pain medications that are administered to patients, who are still in the hospital in real time ([name], Chief Medical Information Officer and [name], CMO at UCHHealth strongly support this project). We have previously shown that 83% of patients after Cesarean section and 71% of thoracic surgery patients report taking half or less of opioids prescribed; 53% and 45% respectively report taking five or less of the prescribed pills. Hence, a “one size fits all” approach to pain management after discharge is common in clinical practice and leads to frequent over-prescription of opioids. Based on our own preliminary data and recommendation published by others, opioids taken 24 hours prior to discharge inform the amount of opioids that are likely to be used at home and hence the following prescriptions amounts have been suggested for patients taking equal or less than 22.5 MME in the 24 hours prior to discharge:

[figure not shown]

Figure 4: Cumulative opioid dose in oral morphine equivalents (OME) prescribed to 652 patients upon hospital discharge after surgery. Clinicians chose the same cumulative opioid dose (300 OME) in more than 75% of patients.

- no opioids for home use for patients having taken no opioids in the last 24 hours prior to discharge
- 75 morphine milligram equivalent (MME), e.g. 10 oxycodone 5mg tablets, for home use for patients having taken equal or less than 22.5 MME, e.g. 1-3 oxycodone 5mg tablets in the last 24 hours prior to discharge.

### IV. Research Methods

#### A. Outcome Measure(s):

Study measurements will include 24 hour prior to discharge opioid and other medication intake, prescribed post-discharge opioid doses in morphine milligram equivalents from the EHR, self-reported analgesic medication requirements (post-discharge intake of opioid medications, left-over opioids, intake of other pain medications, such as acetaminophen and non-steroidal anti-inflammatory drugs – NSAIDs), NIH PROMIS outcomes for Pain Intensity and Pain Interference, side effects, reasons for not taking opioids, as well as basic demographic information. We will also collect information about need for additional opioid prescriptions, and reported medication disposal for left-over opioids, length of hospitalization, repeat vs. first C-section and other relevant perioperative variables. For this study, we will be using REDCap for data collection after Cesarean section to administer four weekly surveys following the day of discharge.

We will seek follow-up with providers about the usefulness and acceptability of the EHR-based intervention. Providers will be surveyed with a REDCap survey using a modified version of the GUIDES checklist, which provides a tool to improve the successful use of guideline-based computerized clinical decision support.

## **B. Description of Population to be Enrolled:**

### **Survey population:**

Inflating enrollment by approximately 25% to account for drop out and result in 44 patient completers, we will consent 60 adult patients receiving a Cesarean section procedure. After completing an observational study in three surgical groups (thoracic surgery, gastrointestinal surgery, C-section), we chose to evaluate this intervention first in C-Section patients based on their unique characteristics: low procedural variability, low incidences of chronic opioid use, and low level of comorbidities. Also, the issue of having potentially unsecured opioids in a household with young children is of special relevance for opioid safety research in the Cesarean section cohort.

Inclusion Criteria: 1) Women ages at least 18 years of age having undergone Cesarean section surgery at the University of Colorado Hospital are eligible. 2) Willingness to complete weekly surveys for 4 weeks after discharge. 3) Anticipated to need half or less of the usually prescribed amount of opioids based on the amount of opioids taken in the last 24 hours prior to the opioid medication being written for discharge (only patients who took 22.5 MME or less opioids in the last 24 hours prior to the day of discharge will be eligible for this study). Inclusion and exclusion criteria (including the amount of opioids taken in the last 24 hours prior to discharge) will be evaluated in the morning in patients scheduled to be discharged later that day.

Exclusion Criteria: 1) Patients under the age of 18 years, 2) Patients returning to institutional settings (e.g. prison, jail, mental health facility), 3) Pregnant women (patients will be approached after their C-section), 4) Decisionally challenged patients, 5) Blind or illiterate patients.

Based on our prior research factors such as emergency status, prior opioid use, repeat vs primary C-section, and associated procedures were not associated with post-discharge opioid use once we adjusted for last-24 hour inpatient opioid use. Hence, these patients will not be excluded.

We will perform a randomized clinical trial (RCT) of an EHR-based recommendation to prescribe opioids at discharge according to the recorded last 24-hour inpatient use according to current recommendations and evaluate its effect on the amount of opioids prescribed as well as pain control after discharge.

The medical provider of each patient enrolled (up to n=60) will also be surveyed using an online REDCap survey. Inclusion criteria: 1) Medical provider of a patient enrolled in the study, 2) Willingness to use the Prescription Tool and complete an online survey. No exclusion criteria.

Total number of participants counting both patients and providers will be 114; up to 60 patients and 54 providers enrolled in the study.

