We will seek a waiver of written consent for surveying providers who are given the dosing suggestion via the EHR-based Prescription Tool. At their convenience, these providers will complete an online postcard consent and survey via REDCap.

After consent, demographics and the best contact information will be collected (remotely by phone during the COVID-19 pandemic or as required by UCHealth) from those enrolled patients who indicate they are interested in completing the surveys after their hospital discharge.

We expect 44 patients to complete all four weekly surveys and we define the intent-to-treat sample as patients who complete one or more surveys (providing at least one observation to be used in analyses). To conservatively allow for increased variability due to attrition, 60 patients will be randomized equally electronically to intervention (prescription tool) or no intervention (prescription as usual). We will use an electronic randomization scheme created so that the principal investigator and statistician can remain blind to assignment.

At the time of writing the prescription for a patient the provider will be informed that a patient may be considered for a lower post-discharge opioid dose (No opioids for patients who did not take any opioids in the last 24 hours, and 10 oxycodone 5mg tablets, for patients having taken less than 22.5 MME, e.g. 1-3 oxycodone 5mg tablets in the last 24 hours). No dosing recommendations for patients having taken more than 22.5 MME will be made as these patients are not eligible for this study. Final dosing decisions and drug choices will remain at the discretion of the treating provider and decisions will be tracked.

For this pilot study, the provider information (best practice alert – BPA) will be operationalized via a written recommendation on paper handed to the provider by study staff in a sealed envelope or emailed with a read receipt that the provider will be asked to open and read. Alternatively, the BPA may be presented electronically using a screen. Providers will be asked to acknowledge that they read the BPA by closing the window or opening the envelope or email.

For the intervention group:

For patients receiving no opioids in the last 24 hours prior to an oxycodone or oxycodone/acetaminophen discharge prescription being written:

**BPA: “In the last 24 hours, your patient received NO opioids. Consider not prescribing any opioids for pain management after discharge.”**

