#### **G. Summarize Knowledge to be Gained:**

We expect to have designed and demonstrated the feasibility of implementation of a decision-making support tool to better estimate individual patient needs for pain therapy after surgery. The instrument will be parsimonious in nature, as it will rely on information that is readily available in the patient's medical record and it will not require any special action by the clinician to obtain a dosage recommendation. Creating such a tool will be critical to translate the findings of this line of research into safer opioid prescribing practices for our patients. Given that the tool can be integrated into a nationally used electronic medical record and order entry system (Epic), usage and further testing of its performance will be possible in many diverse environments. Eventually, public health will be promoted through improving non-opioid analgesia and by decreasing prescriptions of unneeded opioid pain medications. This will lead to a subsequent decreased availability of opioid medications for non-medical use. Further, the data obtained from this aim will be used for a subsequent grant application.

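### The provider acceptability survey admits only providers willing to use the tool, so it is likely to overstate acceptability, by an amount the documents cannot fix

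*Combined protocol and SAP*

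**What the plan says.** Section IV.A (Outcome Measures) states the purpose of the provider survey: "We will seek follow-up with providers about the usefulness and acceptability of the EHR-based intervention". It names the instrument: "Providers will be surveyed with a REDCap survey using a modified version of the GUIDES checklist".

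Section IV.B (Description of Population to be Enrolled) begins broadly: "The medical provider of each patient enrolled (up to n=60) will also be surveyed using an online REDCap survey". It then sets two inclusion criteria. The first is being the provider of an enrolled patient. The second is "Willingness to use the Prescription Tool and complete an online survey". There are no exclusion criteria. The planned total is "up to 60 patients and 54 providers enrolled in the study".

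Section IV.C (Study Design and Research Methods) describes the surveyed group as providers who were given the dosing suggestion, and places their consent together with the survey: "At their convenience, these providers will complete an online postcard consent and survey via REDCap". In the same section, providers are asked to confirm that they read the alert, and prescribing stays with them: "Final dosing decisions and drug choices will remain at the discretion of the treating provider and decisions will be tracked". Section IV.D adds that the tool only suggests, and that both the recommendation and the dose actually prescribed are tracked.

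Section IV.F (Data Analysis Plan) does not mention the provider survey.

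**The concern.** A survey of acceptability should hear from those who found the intervention unacceptable. Willingness to complete a survey is unavoidable in voluntary research. Willingness to use the tool is a separate filter, and it acts on nearly the same attitude that the survey measures. Providers who pass it can be expected to rate the tool more favourably than those who do not.

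What is at stake is the provider-side lesson of a pilot whose data are meant to support a further grant application. Reasons for not engaging with the tool are among the most useful things it could learn, and the criterion works against collecting them. With no plan to count providers who decline, a reader of the results could not judge how selected the respondents were.

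**Working it through.** The documents give no acceptability rate, target or precision for the provider survey, so there is no planned figure to reproduce. The check has three steps.

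**1. What the criterion excludes under each meaning of *use*.** Section IV.B does not define the word.

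| Meaning of *use* | Basis | Who cannot enter the survey |
|---|---|---|
| Following the suggestion | Ordinary reading of the criterion | Every provider who did not follow it |
| Opening and reading the alert | Section IV.C asks only for acknowledgement | Providers unwilling to open or engage with it |

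The excluded group is smaller in the second row, but under both meanings those left out are plausibly less accepting than those admitted.

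**2. Whether anything elsewhere corrects this.**

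- The first sentence on providers in section IV.B covers the provider of each enrolled patient, but the criterion then narrows it.
- Section IV.F compares survey non-completers with completers for patients only.
- No count of providers approached, declining or responding is planned.
- Tracked prescribing decisions (sections IV.C and IV.D) would describe non-followers objectively, but they are not linked to survey answers.
- Section IV.E, on potential scientific problems, does not mention the issue.

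**3. Size.** Let *u* be the share of providers unwilling, *a1* the acceptability among the willing and *a0* the acceptability among the unwilling. The survey, limited to the willing, estimates *a1*. The value for all providers is (1 − *u*)·*a1* + *u*·*a0*. The overstatement is therefore

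*a1* − [(1 − *u*)·*a1* + *u*·*a0*] = *u*·(*a1* − *a0*).

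None of the three inputs is in the documents. For scale only, assume *a1* = 80% and let *a0* run from 40% down to 0%:

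| Assumed *u* | Overstatement, *a0* = 40% | Overstatement, *a0* = 0% | All-provider acceptability |
|---|---|---|---|
| 0% | 0 | 0 | 80% |
| 10% | 0.10 × 40 = 4 points | 0.10 × 80 = 8 points | 76% to 72% |
| 20% | 0.20 × 40 = 8 points | 0.20 × 80 = 16 points | 72% to 64% |
| 30% | 0.30 × 40 = 12 points | 0.30 × 80 = 24 points | 68% to 56% |

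The overstatement is zero if nobody is unwilling, or if the unwilling rate the tool as highly as the willing. Otherwise it is positive whenever the unwilling rate it lower.

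**The case against.** The strongest reply is that *use* here means little more than reading the alert. Section IV.C asks only for acknowledgement, dosing stays with the provider, and section IV.D says the tool does no more than suggest. The criterion also applies to providers of control patients, whose message contains no reduced dose to adopt. On this reading a provider who reads the suggestion and prescribes as usual has used the tool and may be surveyed. This largely stands. It narrows the excluded group to those who would not engage at all, but does not empty it, and the criterion itself does not settle the meaning.

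It also disposes of several stronger inferences that a reader might draw:

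- **That nobody who rejects the suggestion could be heard.** This follows only if use means following.
- **That half of providers are shut out.** The 50% in section IV.F is assumed adoption of the tool by prescribers. Not adopting a dose suggestion is not the same as being unwilling to use the tool, so that figure cannot stand in for *u*.
- **That the trial's feasibility conclusion rests on the survey.** Section IV.G says "We expect to have designed and demonstrated the feasibility of implementation of a decision-making support tool". It speaks of feasibility, not acceptability, and adoption can be read from tracked prescriptions whoever answers the survey.
- **That unwilling providers' patients are lost or cooperative prescribers selected for the trial.** Provider consent comes with the survey, patient eligibility carries no provider condition, and section IV.F compares outcomes needing no survey response in all enrolled patients. Nothing removes a patient because of a provider's attitude.

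A last objection is that voluntary, unpaid participation would leave non-response bias even without the clause. That is true, and it is why the numbers declining should be reported. It is no reason to add a second filter in the same direction.

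**Conclusion.** The concern holds in a limited form. Entry to the usefulness and acceptability survey is conditioned on something close to what it measures, no other section corrects this, and the result is likely to be too favourable. The direction rests on one assumption: that unwilling providers, if there are any, rate the tool lower than willing ones. The size cannot be derived from the documents. On the assumed values shown it runs from 0 to 24 points, and these values illustrate the formula rather than estimate the bias.

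The consequence is confined to the provider survey. The randomised comparison of left-over opioid does not depend on which providers answer it. The change is worth making because it is specific and costs almost nothing.

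**What to change.** - In section IV.B, delete willingness to use the Prescription Tool from the provider criteria, and keep voluntary consent to the survey.
- Invite every provider who was given a tool suggestion, whether or not it was followed. This matches the group described in section IV.C. Reconcile it with section IV.B, which names the provider of each enrolled patient (both arms) and gives both up to 60 and 54 as the number of providers.
- Add a short paragraph to section IV.F: report the numbers invited, declining and responding, and show ratings separately for providers who did and did not follow the suggestion, using the prescribing decisions already tracked. Because the survey is completed once and a provider may have more than one enrolled patient, state in advance how such a provider is classified.

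If the clause is kept, the report should define *use* and say that the ratings describe willing users only.

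The cost is one line of the criteria and a few lines of analysis plan, with a somewhat lower response rate and possibly less favourable ratings. No dose, clinical rule or randomised analysis changes.

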### **C. Study Design and Research Methods**

Using the UCH Epic/Clarity database, we will continuously identify all patients who underwent Cesarean section surgery at University Hospital. Patients will be approached regarding interest in the study prior to hospital discharge. A trained PRA, Perinatal CTRC staff or other trained provider will explain the study to prospective participants using standard language. Participants will be told that they are being asked to be in this research study because they recently had surgery at the University of Colorado Hospital.

If the patient is interested in participation the study PRA, Perinatal CTRC staff or trained provider will review the consent/HIPAA form with the patient and answer any questions the patient may have. Study staff will also provide them with a hard copy of the consent/HIPAA form.

- OR -

**During the SARS-CoV-2 (COVID-19) pandemic** or as required by UHealth, we will minimize in-person contact with patients and complete study visits remotely whenever possible. Perinatal CTRC staff will obtain informed consent from patients using the procedures detailed below.

Consent-HIPAA authorization will be obtained remotely via phone or HIPAA-compliant videoconference application (Zoom) following COMIRB guidance (CG-85, Version April 9, 2020).

- A trained provider with appropriate PPE, who is already providing standard care to the patient, will give the patient a hard copy of the consent/HIPAA form so they have an approved copy of the consent form “in hand” at the time of the informed consent discussion.
- Perinatal CTRC staff will call the patient to initiate the informed consent discussion.
- The discussion will begin with identification of who is participating on the call; Perinatal CTRC staff will confirm the potential subject has a hard copy of the consent-HIPAA form before beginning the discussion.
- Perinatal CTRC staff will review the consent/HIPAA form with the patient and answer any questions.

- The patient will sign the consent-HIPAA form and give it to the trained provider already providing standard care. The provider will give the signed form to Perinatal CTRC staff who will also sign the form noting that consent was obtained by phone. A copy of the signed consent-HIPAA form will be given to the patient.

We will seek a waiver of written consent for surveying providers who are given the dosing suggestion via the EHR-based Prescription Tool. At their convenience, these providers will complete an online postcard consent and survey via REDCap.

After consent, demographics and the best contact information will be collected (remotely by phone during the COVID-19 pandemic or as required by UCHealth) from those enrolled patients who indicate they are interested in completing the surveys after their hospital discharge.

We expect 44 patients to complete all four weekly surveys and we define the intent-to-treat sample as patients who complete one or more surveys (providing at least one observation to be used in analyses). To conservatively allow for increased variability due to attrition, 60 patients will be randomized equally electronically to intervention (prescription tool) or no intervention (prescription as usual). We will use an electronic randomization scheme created so that the principal investigator and statistician can remain blind to assignment.

At the time of writing the prescription for a patient the provider will be informed that a patient may be considered for a lower post-discharge opioid dose (No opioids for patients who did not take any opioids in the last 24 hours, and 10 oxycodone 5mg tablets, for patients having taken less than 22.5 MME, e.g. 1-3 oxycodone 5mg tablets in the last 24 hours). No dosing recommendations for patients having taken more than 22.5 MME will be made as these patients are not eligible for this study. Final dosing decisions and drug choices will remain at the discretion of the treating provider and decisions will be tracked.

For this pilot study, the provider information (best practice alert – BPA) will be operationalized via a written recommendation on paper handed to the provider by study staff in a sealed envelope or emailed with a read receipt that the provider will be asked to open and read. Alternatively, the BPA may be presented electronically using a screen. Providers will be asked to acknowledge that they read the BPA by closing the window or opening the envelope or email.

For the intervention group:

For patients receiving no opioids in the last 24 hours prior to an oxycodone or oxycodone/acetaminophen discharge prescription being written:

**BPA: “In the last 24 hours, your patient received NO opioids. Consider not prescribing any opioids for pain management after discharge.”**

For patients receiving >0 MME up to ≤22.5 MME in the last 24 hours prior to an oxycodone or oxycodone/acetaminophen discharge prescription being written (example BPA is for 15 MME – 2 oxycodone 5mg tablets):

**BPA: “In the last 24 hours, your patient received opioid medication equivalent to 2 oxycodone 5 mg tablets by mouth. Consider writing for a total of 10 oxycodone 5 mg tablets for pain management after discharge.”**

Note, oxycodone-containing medications are the opioid prescribed in >96% of cases after Cesarean section at our hospital. We will make equivalent recommendations if hydrocodone is used. Based on our data, no other opioid medications have been prescribed for use after discharge following Cesarean section.

For the control group:

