**BPA: “Consider prescribing the usual medications for pain management after discharge.”**

One week after hospital discharge interested patients will be contacted and asked to complete the first of four surveys. Participants will receive a \$10 gift card, or equivalent money order if requested, for each of four weekly surveys, for a total of \$40. All enrolled patients will complete the weekly post-discharge surveys within REDCap or by hard copy or phone if they do not have internet access.

Providers will not be paid to use the Prescription Tool or complete the short, one-time online survey.

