For the primary weekly opioid use variable and for secondary longitudinal variables of interest (i.e. weekly scores for pain interference and pain intensity), trajectories will first be visually compared between the two groups. Mixed models will then be used to analyze each outcome that will include fixed group, time, and group by time interaction effects and random patient effects. Covariates will only be included if they differ by group at baseline and are related to the outcome of interest. The test of the group by time interaction will indicate if each outcome differs over time by groups. Overall means for each outcome will be estimated and compared between groups as will week 1 and week 4 means of each outcome will be separately compared between groups. These analyses on the ITT sample will then be repeated on the subset of patients who complete all 4 surveys and any differences between results will be reported.

Important secondary summary variables that will be compared between groups using chi-square, t-test, nonparametric, and covariate-adjusted (i.e. ANCOVA) methods as appropriate are: need for additional opioid prescriptions (yes, no), and amount of opioid and non opioid analgesic drugs taken (total mg). Reported medication disposal by group will additionally be described.

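### No pre-randomisation pain score is named, timed or prespecified as a covariate, so the secondary pain comparison is less precise than it could be and chance imbalance in starting pain goes unseen

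*Combined protocol and SAP*

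**What the plan says.** The hypothesis in Section I has two parts: the tool lowers the amount of opioid prescribed, and pain control does not suffer. Section IV.A measures pain by PROMIS "outcomes for Pain Intensity and Pain Interference" and plans to "administer four weekly surveys following the day of discharge". Section IV.C fixes the first of these: "One week after hospital discharge interested patients will be contacted and asked to complete the first of four surveys". At enrolment, the same section says "After consent, demographics and the best contact information will be collected".

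Section IV.F treats pain among the "secondary longitudinal variables of interest (i.e. weekly scores for pain interference and pain intensity". For these, "trajectories will first be visually compared between the two groups", and then a mixed model is fitted with "fixed group, time, and group by time interaction effects and random patient effects". Overall, week-1 and week-4 means are also compared between arms. On adjustment the rule is: "Covariates will only be included if they differ by group at baseline and are related to the outcome of interest".

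Other baseline information is planned. Section IV.A records opioid and other medication intake in the 24 hours before discharge, plus perioperative variables. The Data and Safety Monitoring Plan draws pain-related clinical values from Epic, without saying which values or from when. Section IV.F compares the arms on baseline demographic and clinical characteristics.

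**The concern.** Starting pain is an obvious candidate predictor of later pain, yet the plan names no measure of it before randomisation. Three things follow.

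- The pain comparison gives up the precision that adjustment for starting pain would bring. This matters because a claim that pain control is maintained rests on a narrow interval around the difference, and the trial expects only 44 completers.
- The covariate rule in Section IV.F cannot be applied to starting pain as the plan is written, because no named score exists to test for imbalance or to include. Opioid intake in the last 24 hours is only a proxy, and eligibility confines it to 0 to 22.5 MME.
- The first point on the pain trajectories is week 1, so the plots and the group-by-time test describe change from week 1, not from discharge.

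**Working it through.** **The plan's own sample size.** Section IV.F gives left-over means of 101.8 (SD 60.5) and 55 (SD 37.6) MME, a one-tailed alpha of 0.05, a Mann-Whitney test and 22 per group for 90% power.

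- Difference: 101.8 − 55 = 46.8. Pooled SD: √((60.5² + 37.6²)/2) = 50.37. Effect size: 46.8/50.37 = 0.929.
- With Mann-Whitney efficiency 3/π = 0.955, the noncentrality at n = 22 is 0.929 × √(22 × 0.955/2) = 3.01 on 2 × 22 × 0.955 − 2 = 40 degrees of freedom. Power is 90.6%, and 22 is the smallest n that reaches 90%.

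The figure reproduces. It concerns left-over opioid and does not depend on a pain baseline. The protocol states no power for pain.

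**Order of events.** Eligibility is checked on the morning of discharge (Section IV.B). Randomisation must precede the provider alert, which comes when the prescription is written (Section IV.C). The first PROMIS score follows one week after discharge. No pain score is named before randomisation.

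**Precision.** Let r be the correlation between starting pain and the follow-up score. In an ANCOVA with one follow-up, residual variance is multiplied by 1 − r² and the standard error by √(1 − r²). The protocol does not give r; I assume 0.3 to 0.6. In units of the pain SD, the 95% half-width is 1.96 × √(2/n) × √(1 − r²). The difference detectable with 80% power at two-sided 0.05 is (1.96 + 0.842) × √(2/n) × √(1 − r²). Both use the normal approximation.

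| r | variance factor | SE factor | half-width, 22 per arm | detectable, 22 per arm | detectable, 30 per arm |
|---|---|---|---|---|---|
| none | 1 | 1 | 0.591 | 0.845 | 0.723 |
| 0.3 | 0.91 | 0.95 | 0.564 | 0.806 | 0.690 |
| 0.5 | 0.75 | 0.87 | 0.512 | 0.732 | 0.626 |
| 0.6 | 0.64 | 0.80 | 0.473 | 0.676 | 0.579 |

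The 22 per arm are the expected completers. The 30 per arm apply if all 60 randomised patients return at least one survey.

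**Chance imbalance.** The difference in mean starting pain between arms has SD √(2/n): 0.302 at 22 per arm and 0.258 at 30. The chance that it exceeds 0.3 SD in either direction is 2 × (1 − Φ(0.3/0.302)) = 32%, and 25% at 30 per arm. An imbalance of 0.3 SD shifts the expected follow-up difference by r × 0.3, which is 0.09 to 0.18 SD for r from 0.3 to 0.6.

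**The interaction test.** Suppose the arms differ by a constant δ in weeks 1 to 4. The group-by-time interaction is then zero, while the overall and week-1 mean differences both equal δ. A baseline covariate in the same model changes the precision of those mean differences. It does not make the interaction sensitive to δ.

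**The case against.** The strongest reply is that nothing here is an error. With 1:1 randomisation, the week 1 to 4 comparison is valid without a baseline, and the unadjusted standard error already allows for chance imbalance in starting pain. Pain is a secondary outcome in what Section IV.C calls a pilot. All of that stands, and it limits the point to precision.

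Several stronger readings are tempting, and the documents do not support them.

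- *The pain comparison cannot be adjusted for starting pain.* The plan takes pain-related values from Epic, and an inpatient score may be among them. The gap is that none is named, timed or placed in the model.
- *Only demographics and contact details are collected at baseline.* The Section IV.C sentence does not say only, and Section IV.A and the Data and Safety Monitoring Plan add record data.
- *An early, lasting difference would be missed.* The interaction test would miss it, but Section IV.F already plans overall and week-1 mean comparisons, which would not. Nor would a baseline covariate change what the interaction tests.
- *Most opioid use is over before the first survey.* The assumed control total is 150 − 101.8 = 48.2 MME, or 6.4 tablets of 150/20 = 7.5 MME. The protocol gives no time course for that use and no recall period for the pain items, so this is conjecture.

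The gain is also uncertain. The correlation is assumed, and at 0.3 the standard error falls by only about 5%. The formula describes one follow-up, whereas the plan fits four visits; for the overall mean, r would be the correlation with each patient's four-week average. The formula also ignores the small cost of estimating one more coefficient, so the lower end is slightly generous.

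**Conclusion.** The point holds as a cheap improvement, not as a flaw that threatens validity. No pre-randomisation pain score is named or prespecified as a covariate, and the rule in Section IV.F would admit one only after an observed imbalance. The week 1 to 4 comparison stays unbiased, and the primary outcome with its 22 per group is unaffected.

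The cost is a less precise pain comparison and no view of chance imbalance in starting pain, which would exceed 0.3 SD about 25 to 32% of the time. For an assumed correlation of 0.3 to 0.6, adjustment would cut residual variance by about 9 to 36% and the standard error by about 5 to 20%. These figures rest on that assumed range and on the single-follow-up approximation.

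**What to change.** - Give the PROMIS Pain Intensity and Pain Interference items used in the weekly surveys once, after consent and before randomisation, in both arms. Alternatively, name one specific Epic pain score and its time window before randomisation. Use a single instrument for all patients, without substituting one for the other.
- In Section IV.F, state that this score enters the pain mixed models as a prespecified covariate whether or not the arms differ on it, in place of the imbalance-triggered rule for this variable. State how a missing baseline score will be handled.
- State that pain control will be judged from the adjusted overall and week-1 mean differences with their confidence intervals, not from the group-by-time interaction alone.
- Show the baseline score by arm with the other baseline characteristics.

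The cost is a few minutes of patient time at a contact that already takes place, by phone where consent is remote, plus a few lines in the analysis plan. Sample size and primary analysis do not change.
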